6.6.2 Paternal exposure

Time period for restricting procreation after end of study is set at $\times 5$ half-lives plus 2 weeks.

Male patients should refrain from fathering a child or donating sperm during the study and for 30 days following the last dose.

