3.1 Inclusion criteria

For inclusion in the study patients should fulfill the following criteria:

1. Is willing and able to give written informed consent prior to any study specific procedures;
2. Has diagnosis of T2DM treated with a stable dose of metformin (≥ 1500 mg/day), as monotherapy for at least 8 weeks prior to Screening;
3. Has a body mass index (BMI) ≤ 45 kg/m²;
4. Has an HbA1c $\geq 7\%$ and $\leq 10\%$ obtained at Screening;
5. Has a fasting C-peptide concentration ≥ 1.0 ng/mL at Screening;
6. Is male or female, ages 18 to 75 years, inclusive;
7. Women of childbearing potential (WOCBP), defined as any female who has experienced menarche and who has not undergone surgical sterilization (hysterectomy or bilateral oophorectomy), must agree to use 2 medically accepted, effective methods of birth control (e.g., hormonal contraceptive, barrier contraceptive with additional spermicide, or an intrauterine device) beginning >30 days prior to study drug administration and continuing for 3 months after the end of the study;

8. Women must have a negative serum or urine pregnancy test (minimum sensitivity 25 IU/L or equivalent units of human chorionic gonadotropin [HCG]) within 24 hours prior to the start of investigational product;
9. Women must not be breastfeeding;
10. Males who are sexually active with WOCBP must be surgically sterile or using an acceptable method of contraception (defined as barrier methods in conjunction with spermicides) for the duration of the study (from the time they sign consent) and for 3 months after the last dose of study medication to prevent pregnancy in a partner;
11. Women who are not of childbearing potential (i.e., who are postmenopausal or surgically sterile) and azoospermic men do not require contraception. For this study, menopause is defined clinically as 12 months of amenorrhea in a woman over age 45 in the absence of other biological or physiological causes. In addition, women under the age of 62 must have a documented serum follicle-stimulating hormone (FSH) level >40 mIU/mL. Women treated with hormone replacement therapy (HRT) are likely to have artificially suppressed FSH levels and may require a washout period in order to obtain a physiologic FSH level. The duration of the washout period is a function of the type of HRT used:
- 1 week minimum for vaginal hormonal products (rings, creams, gels),
 - 4 week minimum for transdermal products,
 - 8 week minimum for oral products,

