4.3 Follow-up period

4.3.1 Safety follow-up visit, 4 weeks after Day 70 visit

Patients will arrive at the study site for a safety follow-up visit. Assessments for the follow-up visit are outlined in [Table 2](#).

Samples will be taken from patients for safety laboratory assessments. See [Table 4](#) for a list of the safety laboratory variables.

At this visit, IVRS/IWRS should be contacted to document study completion.

Note: other treatments during the 4 weeks of follow-up after Day 70 can be initiated.

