7.2 Dose and treatment regimens

Double-blind study medication will be administered subcutaneously once weekly (Day 7 each week). The IVRS/IWRS, described in Section 3.5, will be used to assign each patient EQW or placebo, at the appropriate dispensing visits.

Patients will take their first dose of double-blind study medication (EQW or placebo) at the site on Day 1. The time of first dose will be noted on the eCRF. Patients will be trained on IP administration at this visit. The injection must be administered immediately after preparation of the dose.

During the treatment period, patients will take the double-blind study medication once weekly (Day 7 each week). Patients will take metformin XR once daily with the evening meal.

The study design includes the following 2 treatment periods:

Medical nutrition and metformin XR lead-in period

After qualifying for entry into the lead-in period, patients will discontinue their current metformin therapy and begin a 4-week, medical nutrition, and open-label metformin XR lead-in period. Patients will be given pharmacy cards to obtain metformin XR. The dose of metformin XR assigned will correspond with each patient's background dose of metformin. Each patient will be instructed to take:

- Open-label metformin XR: 3-4 tablets with the evening meal (1500-2000 mg)

Compliance with the administration of multiple tablets will be assessed during the lead-in period. Patients must demonstrate good compliance (see Section 7.5) with metformin XR (80% to 120%) during the lead-in period and the ability to have a week-long CGM measurement to be eligible for randomization.

Double-blind treatment period

Following completion of the lead-in period, eligible patients will enter the 10-week, double-blind treatment period.

Patients will be randomized to 1 of 2 treatment arms:

- EQW + open-label metformin XR (1500-2000 mg).
- Placebo + open-label metformin XR (1500-2000 mg).

The double-blind study medication (either EQW or placebo) will be administered subcutaneously once weekly and the metformin XR will be taken once daily with the evening meal.

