9.3 Study timetable and end of study

The end of the study is defined as ‘the last visit of the last patient undergoing the study’.

The study is expected to start in the 4th quarter 2014 and to end by 4th quarter 2015.

The study may be terminated at individual centers if the study procedures are not being performed according to Good Clinical Practice (GCP), or if recruitment is slow. AstraZeneca may also terminate the entire study prematurely if concerns for safety arise within this study or in any other study with BYDUREON.

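### Male contraception after the last dose: inclusion criterion 10 says 3 months, Section 6.6.2 says 30 days, and a further period in 6.6.2 has no usable length

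*Protocol*

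**What the plan says.** The protocol restricts conception by male patients in two places.

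- **Section 3.1, inclusion criterion 10.** "Males who are sexually active with WOCBP must be surgically sterile or using an acceptable method of contraception", from consent through the study and then "for 3 months after the last dose of study medication to prevent pregnancy in a partner". Criterion 11 exempts azoospermic men.
- **Section 6.6.2, second sentence.** "Male patients should refrain from fathering a child or donating sperm during the study and for 30 days following the last dose".
- **Section 6.6.2, first sentence.** "Time period for restricting procreation after end of study is set at" five half-lives plus two weeks. The protocol gives no half-life for exenatide or for the formulation.

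Three other statements are needed to place these periods on the study calendar. Section 7.2: "Patients will take their first dose of double-blind study medication (EQW or placebo) at the site on Day 1", with weekly dosing after that. The heading of Section 4.3.1: "Safety follow-up visit, 4 weeks after Day 70 visit". Section 9.3: "The end of the study is defined as" the final visit of the final patient, not the individual patient's own last visit.

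**The concern.** A restriction on conception after exposure is a safety instruction that site staff give to patients. Here the eligibility section and the safety section give different lengths from the same starting event, and no rule of precedence links them. Section 3 allows no exceptions to eligibility, so a site that counsels men from 6.6.2 alone gives advice that departs from an inclusion criterion. About 30 sites are planned, so it is realistic that different sites will work from different sections.

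At stake is the protection of partners and the consistency of what men are told. No endpoint, sample size, error rate or analysis depends on it.

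**Working it through.** This is a comparison of text with calendar arithmetic. The plan gives no figure of its own to reproduce.

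**Inputs**
- Criterion 10: 3 months from last dose, taken as 90 to 92 days.
- Section 6.6.2, second sentence: 30 days from last dose.
- Section 6.6.2, first sentence: 14 days + 5*h* from end of study, where *h* is the half-life in days. It is left free because the protocol states none.
- Last dose: ten weekly doses from Day 1 give Day 1 + 9 × 7 = Day 64. Day 63 and Day 70 are used as alternatives, because dosing is also described as falling on Day 7 of each week. These days are an assumption.
- Patient's own last visit: Day 70 + 28 = Day 98.

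**Step 1. The two periods counted from last dose**

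| Last dose | 30 days ends | 3 months ends | Gap |
|---|---|---|---|
| Day 63 | 63 + 30 = Day 93 | Day 153 to 155 | 60 to 62 days |
| Day 64 | 64 + 30 = Day 94 | Day 154 to 156 | 60 to 62 days |
| Day 70 | 70 + 30 = Day 100 | Day 160 to 162 | 60 to 62 days |

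The gap depends neither on the last-dose day nor on any half-life. With a last dose on Day 63 or 64, the 30 days are over before the patient's own Day 98 visit.

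**Step 2. Can the half-life sentence reconcile them?**
Read end of study generously as the patient's own last visit. The period then ends on Day 98 + 14 + 5*h* = Day 112 + 5*h*.
- To match 30 days: *h* = (93 − 112)/5 = −3.8 to (100 − 112)/5 = −2.4. A negative half-life is impossible.
- To match 3 months: *h* = (153 − 112)/5 = 8.2 to (162 − 112)/5 = 10.0 days.

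Now count it from the last dose, which is not what the sentence says.
- To match 30 days: *h* = (30 − 14)/5 = 3.2 days.
- To match 3 months: *h* = (90 − 14)/5 = 15.2 to (92 − 14)/5 = 15.6 days.

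No single half-life gives both periods under either start point. Read with the Section 9.3 definition, the sentence also has no start date that a patient could know when he leaves the study.

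**The case against.** Four counter-arguments deserve an answer.

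1. **The rules differ in kind and are not mutually exclusive.** Criterion 10 is about contraception; 6.6.2 is about fathering a child and donating sperm. A man who uses contraception for 3 months also stays within the 30-day limit on fathering. This stands, and it rules out the stronger inference that no consistent instruction could be given. It does not remove the mismatch: both rules aim to prevent conception after exposure, and they release the man at different times.

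2. **The half-life sentence may be damaged or may only be a general rule.** The text reads "Time period for restricting procreation after end of study is set at $\times 5$ half-lives plus 2 weeks", with a multiplication sign and nothing before it. That may be a conversion fault or a template remnant. The next sentence could be its applied value, which would need a half-life of 3.2 days counted from the last dose. That cannot be shown from the document, and the sentence names end of study as its start. The firm conflict is therefore 30 days against 3 months, and it stands without this sentence.

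3. **Section 6.6.2 also covers the study itself.** If that runs to the patient's Day 98 visit, the restriction in 6.6.2 ends on Day 98 for a last dose on Day 63 or 64. The gap to criterion 10 is then 153 − 98 = 55 to 156 − 98 = 58 days, still about eight weeks. If the study means the whole trial as in Section 9.3, the end date is unknown to the individual man and the sections still disagree.

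4. **Consent wording may already settle it.** The consent pages are not in the available text, so nothing can be said about what patients were told. Only the protocol text is at fault here.

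A reader might also infer that the period for following pregnancies in partners is left unclear. The protocol does not support this: Section 6.6 asks for all pregnancies to be reported, sets no time limit and ties nothing to the contraception window.

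**Conclusion.** The protocol contradicts itself and is wrong as written on this point. From the same start point, 6.6.2 is about 60 days shorter than criterion 10 (about eight weeks if its restriction is taken to last until the patient's Day 98 visit). The half-life sentence yields no duration and cannot bring the two into line.

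The 60-day figure rests only on the two stated periods and on 3 months being 90 to 92 days. The study-day positions rest on the assumed last-dose day.

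The contradiction does not reach every male patient. It concerns men who are neither surgically sterile nor azoospermic and who have partners of childbearing potential. Which period is right is not judged here. It should be corrected because sites act on it, but it has no bearing on the trial's statistical conclusions.

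**What to change.** Reconcile inclusion criterion 10 and Section 6.6.2 so that both give one period, in days, from one start point defined for the individual patient. State whether it covers contraception, fathering and sperm donation alike. Either remove the half-life sentence or give it a stated value and a start point that agree with that period. The sponsor's safety function must choose the period. Check that the consent wording matches.

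The cost is a protocol clarification, with ethics review of the consent form if its wording changes. Enrollment targets and analyses are unaffected.

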6.7 Management of IP related toxicities

Dose reductions of the study medication are not permitted in this study.

6.8 Study governance and oversight (Not applicable)

7. INVESTIGATIONAL PRODUCT AND OTHER TREATMENTS

7.1 Identity of investigational product(s)

All study drugs will be provided to the sites by AstraZeneca.

All IPs will be packed into kits containing enough IP for 4 weeks of treatment. The vials contained exenatide/placebo powder for injections will be packed into a small box containing 4 vials. Four syringes with diluent for suspension of EQW and matching placebo will be packed into another box also containing 6 vial adapters and six 23-gauge \times 5/16 inch needles.

Metformin will be supplied via pharmacy cards through a pharmacy.

If a patient is on 1500 mg of metformin XR at screening, they will receive 1500 mg metformin XR during the lead-in period. If a patient is on 2000 mg of metformin XR at screening, they will receive 2000 mg metformin XR during the lead-in period. Patients on 2500 mg or 2550 mg of metformin XR daily (850 mg TID) will receive 2000 mg of metformin XR.

Study drugs will only be dispensed to patients in accordance with the protocol. [Table 5](#) presents the investigational products used in this study.

Table 5 Identity of investigational products

Investigational product	Dosage form and strength	Manufacturer
Exenatide once weekly (EQW)	2.0 powder for injection	AstraZeneca
Placebo to match exenatide once weekly	Placebo powder for injection	AstraZeneca

7.2 Dose and treatment regimens

Double-blind study medication will be administered subcutaneously once weekly (Day 7 each week). The IVRS/IWRS, described in Section 3.5, will be used to assign each patient EQW or placebo, at the appropriate dispensing visits.

Patients will take their first dose of double-blind study medication (EQW or placebo) at the site on Day 1. The time of first dose will be noted on the eCRF. Patients will be trained on IP administration at this visit. The injection must be administered immediately after preparation of the dose.

During the treatment period, patients will take the double-blind study medication once weekly (Day 7 each week). Patients will take metformin XR once daily with the evening meal.

The study design includes the following 2 treatment periods:

Medical nutrition and metformin XR lead-in period

After qualifying for entry into the lead-in period, patients will discontinue their current metformin therapy and begin a 4-week, medical nutrition, and open-label metformin XR lead-in period. Patients will be given pharmacy cards to obtain metformin XR. The dose of metformin XR assigned will correspond with each patient's background dose of metformin. Each patient will be instructed to take:

- Open-label metformin XR: 3-4 tablets with the evening meal (1500-2000 mg)

Compliance with the administration of multiple tablets will be assessed during the lead-in period. Patients must demonstrate good compliance (see Section 7.5) with metformin XR (80% to 120%) during the lead-in period and the ability to have a week-long CGM measurement to be eligible for randomization.

Double-blind treatment period

Following completion of the lead-in period, eligible patients will enter the 10-week, double-blind treatment period.

Patients will be randomized to 1 of 2 treatment arms:

- EQW + open-label metformin XR (1500-2000 mg).
- Placebo + open-label metformin XR (1500-2000 mg).

The double-blind study medication (either EQW or placebo) will be administered subcutaneously once weekly and the metformin XR will be taken once daily with the evening meal.

7.3 Labeling

Labels will be prepared in accordance with Good Manufacturing Practice (GMP) and local regulatory guidelines. The labels will fulfill GMP Annex 13 requirements for labeling. Label text will be translated into local language.

7.4 Storage

All study drugs should be kept in a secure place under appropriate storage conditions. The IP label on the study medication kit specifies the appropriate storage.

7.5 Compliance

The administration of all study drugs (including investigational products) should be recorded in the appropriate sections of the eCRF.

Each time study medication is dispensed, compliance will be reinforced. When study medication is returned, compliance will be assessed based on an interview with the patient and a count of the tablets of metformin XR returned which should be between 80% to 120% of that prescribed. During the treatment period, compliance with EQW will be assessed by reviewing the used vials. Patients will be asked to bring their used vials into the site visit. The Investigator (or designee) will record the amounts of study medication dispensed and returned at each visit and the dates of any study drug interruption. If the patient is not between 80% to 120% compliant with open-label metformin XR during the lead-in period, the patient will not be eligible for randomization. If the patient is not between 80% to 120% compliant during the double-blind treatment period, the period of noncompliance should be noted as a protocol deviation and AstraZeneca should be notified. The patient should be educated regarding the schedule for taking study drug.

7.6 Accountability

The study drug provided for this study will be used only as directed in the study protocol.

For this study, study drugs (those supplied by AstraZeneca or sourced by the Investigator) such as partially used study drug containers, vials, and syringes may be destroyed on site.

Any unused study drugs can only be destroyed after being inspected and reconciled by the responsible AstraZeneca Study Monitor unless study drug containers must be immediately destroyed as required for safety, or to meet local regulations (e.g., cytotoxics or biologics).

On-site destruction is allowed provided the following minimal standards are met:

- On-site disposal practices must not expose humans to risks from the drug.
- On-site disposal practices and procedures are in agreement with applicable laws and regulations, including any special requirements for controlled or hazardous substances.
- Written procedures for on-site disposal are available and followed. The procedures must be filed with the site's standard operating procedures and a copy provided to AstraZeneca upon request.
- Records are maintained that allow for traceability of each container, including the date disposed of, quantity disposed, and identification of the person disposing the containers. The method of disposal, i.e., incinerator, licensed sanitary landfill, or licensed waste disposal vendor must be documented.
- Accountability and disposal records are complete, up-to-date, and available for the Monitor to review throughout the clinical trial period.

If conditions for destruction cannot be met, the responsible Study Monitor will make arrangements for destruction of study drug.

It is the Investigator's responsibility to arrange for disposal of all empty containers, provided that procedures for proper disposal have been established according to applicable federal, state, local, and institutional guidelines and procedures, and provided that appropriate records of disposal are kept.

7.7 Concomitant and other treatments

Patients will be allowed to use any other concomitant medications they require during the study except: systemic glucocorticoid therapy of greater than 14 consecutive days' duration (with the exception of topical, intraocular, and inhaled preparations).

Patients will not be allowed to use acetaminophen or paracetamol during the study, as these two drugs may interfere with the CGM device.

Patients will continue metformin XR during the study. Patients should discontinue other oral anti-hyperglycemic mediations at least 4 weeks prior to screening. The intent of this study is that patients do not deviate from their metformin regimen. However, in emergencies, it may be necessary for patients to change their dose of metformin XR. This is allowed for up to 7 consecutive days or up to 7 days within a month. If such a situation occurs more than once during the study or lasts longer than 7 consecutive days or more than 7 days within a month, a decision to keep the patient in the study should be made only after consultation between the Investigator and the AstraZeneca clinical research physician. The decision should be documented by a note to the Investigator's file.

Patients must follow the medication restrictions outlined in the inclusion and exclusion criteria (Section 3.1 and Section 3.2, respectively) during the study. Dosages for certain concomitant medications should remain constant during the study unless instructed otherwise by the Investigator or treating physician. Any change in regimen for any concomitant medication, including restricted concomitant medications, must be reported to the Sponsor.

Table 6 lists the prohibited medications and the applicable time frames for this study.

Table 6 Restricted medications

Restricted medication/class of drug	Usage
Anti-hypertensive agents	Patient must either not be treated with or has been on a stable treatment regimen for a minimum of 2 months prior to Screening.
Thyroid replacement therapy	Patient must either not be treated with or has been on a stable treatment regimen for a minimum of 2 months prior to Screening.
Anti-depressant agents	Patient must either not be treated with or has been on a stable treatment regimen for a minimum of 2 months prior to Screening.
Exenatide (including Byetta [®] , Bydureon [™] , or exenatide suspension) or any GLP-1 analog	Exposure 6 months prior to Screening is prohibited (or use of non-study products during the study).
Dapagliflozin (FORXIGA, FARXIGA) or any SGLT-2 inhibitor	Exposure 8 weeks prior to Screening is prohibited (or use of non-study products during the study).
Thiazolidinedione	Exposure 12 weeks prior to Screening is prohibited.
Any DPP-4 inhibitor	Prohibited 12 weeks prior to Screening and during the study.
Pramlintide (SYMLIN [®])	Prohibited within 3 months prior to Screening and during the study.

Table 6 Restricted medications (Continued)

Restricted medication/class of drug	Usage
Systemic corticosteroids by oral, intravenous, intra-articular, or intramuscular route	Patient must not have received either repeated acute intermittent corticosteroid treatment or non-replacement corticosteroid therapy for longer than 7 consecutive days during the 4 weeks prior to Screening. Stable replacement corticosteroid treatment administered for at least 4 weeks prior to Screening is allowed.
Potent, inhaled, or intrapulmonary (including ADVAIR®) steroids known to have a high rate of systemic absorption beclomethasone dipropionate nasal and oral inhalation (Beclovent, Beconase, Qnasl, QVAR) budesonide nasal and oral inhalation (Pulmicort, Symbicort, Rhinocort) flunisolide oral inhalation aerosol and nasal route (AeroBid, Aerospan, Nasalide, Nasarel) fluticasone propionate aerosol and powder (Advair, Flovent) mometasone furoate aerosol and powder inhalation (Asmanex, Dulera)	Prohibited within 3 months prior to Screening and during the study.
Prescription or over-the-counter weight loss medications	Prohibited within 3 months prior to Screening and during the study.

Note: This is not a comprehensive listing. If the exclusion status of any concomitant medication is in question, please contact the medical monitor for discussion. The following steroids are permitted during the study: ciclesonide oral inhalation and nasal spray (Alvesco, Omnaris, and Zetonna).

